5.1. Disposition

For Part A, the following will be summarized for all enrolled participants:

- The number of participants randomized.

For Part A, the following will be summarized for the participants in the safety set, by treatment sequence and overall:

- The number of participants who received plixorafenib alone in a fasted state.
- The number of participants who received plixorafenib and cobicistat in a fasted state.
- The number of participants who received plixorafenib and cobicistat in a fed state.
- The number of participants who were treated in treatment period 1.

- The number of participants who were treated in treatment period 2.
- The number of participants who were treated in treatment period 3.
- The number of participants who completed treatment period 1.
- The number of participants who did not complete treatment period 1 (both overall and according to reasons for discontinuation from the treatment period 1).
- The number of participants who completed treatment period 2.
- The number of participants who did not complete treatment period 2 (both overall and according to reasons for discontinuation from the treatment period 2).
- The number of participants who completed treatment period 3.
- The number of participants who did not complete treatment period 3 (both overall and according to reasons for discontinuation from the treatment period 3).
- The number of participants who completed the study.
- The number of participants who did not complete the study (both overall and according to reasons for discontinuation from the study).
- The number of participants in the safety and PK analysis sets.

For Part B, the following will be summarized for the participants in the safety set, by treatment sequence and overall:

- The number of participants who received plixorafenib alone in a fasted state.
- The number of participants who received plixorafenib alone after a low-fat meal.
- The number of participants who received plixorafenib alone after a high-fat meal.
- The number of participants who received plixorafenib and cobicistat after a low-fat meal.
- The number of participants who were treated in treatment period 1.
- The number of participants who were treated in treatment period 2.
- The number of participants who were treated in treatment period 3.

- The number of participants who completed treatment period 1.
- The number of participants who did not complete treatment period 1 (both overall and according to reasons for discontinuation from the treatment period 1).
- The number of participants who completed treatment period 2.
- The number of participants who did not complete treatment period 2 (both overall and according to reasons for discontinuation from the treatment period 2).
- The number of participants who completed treatment period 3.
- The number of participants who did not complete treatment period 3 (both overall and according to reasons for discontinuation from the treatment period 3).
- The number of participants who completed the study.
- The number of participants who did not complete the study (both overall and according to reasons for discontinuation from the study).
- The number of participants in the safety and PK analysis sets.

Participant disposition data will be presented in a data listing.

5.2. Protocol Deviations

A protocol deviation is any change, divergence, or departure from the study design or procedures defined in the protocol. An important deviation (sometimes referred to as a significant or major deviation) is a subset of protocol deviations that leads to a participant being discontinued from the study, or significantly affects the participant's rights, safety, or well-being and/or the completeness, accuracy, and reliability of the study data. An important deviation can include nonadherence to inclusion or exclusion criteria or nonadherence to FDA regulations or International Council for Harmonization (ICH) E6(R2) guidelines.

Important protocol deviations will be summarized overall for participants in the safety set. All protocol deviations will be presented in a data listing.

5.3. Inclusion and Exclusion Criteria

Admission criteria deviations will be presented in a data listing.

6. Demographics and Baseline Characteristics

6.1. Demographics

Demographic information collected at screening will be presented in a data listing.

Descriptive statistics will be calculated for the following continuous demographic characteristics collected at screening:

- Age (years)
- Weight (kg)
- Height (cm)
- Body mass index (BMI) (kg/m²)

Frequency counts and percentages will be tabulated for the categorical variables:

- Sex
- Race
- Ethnicity

The summaries will be presented by treatment sequence overall for participants in the safety set.

6.2. Medical History

The medical history data will be coded using the Medical Dictionary for Regulatory Activities (MedDRA, version to be delineated in the clinical study report [CSR]) and presented in a data listing.

7. Treatments and Medications

7.1. Prior and Concomitant Medications

Medications that stop prior to the first dose of any study drug will be classified as prior medication. Medications that start on or after the first dose of any study drug will be classified as concomitant. If a medication starts before the first dose of any study drug and stops on or after the first dose of any study drug, then the medication will be classified as both prior and concomitant.

All prior and concomitant medications will be coded according to the World Health Organization Drug Dictionary (version to be delineated in the CSR) and presented in a data listing.

7.2. Study Treatment

The study drug administration and drug accountability data as collected on eCRF will be presented in the data listings.

A data listing detailing meal information will also be presented.

8. Safety Analysis

All safety summaries and analyses will be based upon the safety set.

8.1. Adverse Events

An adverse event (AE) is defined as any untoward medical occurrence associated with the use of a drug in humans, whether or not considered drug related.

A treatment emergent AE (TEAE) is defined as any event not present before exposure to study drug or any event already present that worsens in severity or frequency after exposure.

An AE is considered a serious AE (SAE) if, in the view of either the investigator or sponsor, it results in any of the following outcomes:

- Death
- Life-threatening AE
- Inpatient hospitalization or prolongation of existing hospitalization
- Persistent or significant incapacity or substantial disruption of the ability to conduct normal life functions
- Congenital anomaly or birth defect

Important medical events that may not result in death, be life threatening, or require hospitalization may be considered serious when, based upon appropriate medical judgment, they may jeopardize the participant and may require medical or surgical intervention to prevent one of the outcomes listed in this definition.

The AE's relationship to study treatment will be evaluated by the investigator. The following relationships will be collected on eCRF: probably related, possibly related, or not related. The AEs that are evaluated as probably or possibly related will be considered treatment-related AEs for summary purpose.

The severity of AEs will be classified by the investigator as mild, moderate, or severe, and AEs will also be graded based on Common Toxicity Criteria for Adverse Events (CTCAE) V5.0.

Adverse events of special interest (AESIs) will be identified by the investigator on the eCRF. AESIs include:

- Grade ≥ 2 increased bilirubin
- Grade ≥ 2 increased alanine aminotransferase (ALT)
- Grade ≥ 2 increased aspartate aminotransferase (AST)

An overall AE summary will be generated presenting the frequency and percentage of participants and the number of AEs, by treatment and the overall population, for the following:

- (For Part A Only) Any AE (presented by overall only)
- Any TEAE
- Any TEAE related to Plixorafenib
- Any TEAE related to Cobicistat
- Any Grade ≥ 3 TEAE
- Any SAE
- Any TEAE leading to study drug discontinuation
- Any TEAE leading to early study discontinuation
- Any AESI
- Any Death

All AEs will be coded using MedDRA (version to be delineated in the CSR). The TEAEs will also be summarized, by treatment and overall population, by system organ class (SOC), preferred term (PT), by CTCAE toxicity grade, and either:

- Part A: by Relationship to study treatment.
- Part B: or for related TEAEs only.

Treatment Emergent AESIs will also be presented by SOC and PT, by treatment and overall.

An additional table will summarize the TEAEs by treatment sequence and overall, by SOC and PT.

The TEAE summary tables will be sorted by SOC and PT. System organ class will be displayed alphabetically. Preferred term will be displayed in descending order of overall frequency and then alphabetically within SOC. A participant with 2 or more events within the same level of summarization will be counted only once in that level using the highest CTCAE grade, or most related incident (for Part A summary by relationship only). Percentages will be based on the number of participants in the safety set.

All AEs will be presented in a data listing. Separate data listings will be generated for treatment related AEs, AESIs, SAEs, and AEs leading to treatment discontinuation.

For Part A and B, a TEAE will be assigned to the last treatment received prior to the assessment/observation as below:

- Treatment received in Treatment Period 1 if the AE start date/time is on or after the first dose of study drug in the Treatment Period 1, but prior to the first dose of study drug in Treatment Period 2.
- Treatment received in Treatment Period 2 if the AE start date/time is on or after the first dose of study drug in the Treatment Period 2, but prior to the first dose of study drug in Treatment Period 3.
- Treatment received in Treatment Period 3 if the AE start date/time is on or after the first dose of study drug in the Treatment Period 3.

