## **6.2 SAFETY ASSESSMENTS AND ENDPOINTS**

Safety will be assessed by the following: monitoring and recording of AEs, clinical laboratory test results (hematology, serum chemistry, and urinalysis), vital sign measurements, 12-lead ECG results, and physical examination findings.

For all safety assessments, the investigator will determine whether results are clinically significant, which is defined as any variation in a result that has medical relevance or may result in an alteration in medical care (eg, active observation, diagnostic measures, or therapeutic measures). If clinical significance is noted, the result and reason for significance will be documented and an AE reported on the AE page of the participant's eCRF. The investigator will monitor the participant until the result has reached the reference range or the result at screening, or until the investigator determines that follow-up is no longer medically necessary.

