### **6.2.1 Sponsor Communication**

The sponsor Medical Monitor will be contacted as quickly as possible for Grade 2 or above changes in blood AST, ALT, GGT, bilirubin (total or fractionated), or creatinine, or  $\geq$  Grade 3 laboratory abnormalities or adverse events. Communication with the sponsor Medical Monitor should not delay immediate management of the participant.

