## 6.2.2 Adverse Events

Adverse events will be assessed from the time the participant signs the ICF until EOS and should be followed until they are resolved, stable, or judged by the investigator to be not clinically significant.

The investigator is responsible for ensuring that all AEs and SAEs are recorded in the eCRF and reported to the sponsor, regardless of their relationship to study drug or clinical significance. If there is any doubt as to whether a clinical observation is an AE, the event should be reported.

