#### **6.2.2.6 Adverse Event of Special Interest**

The following are AESIs for this study:

- Grade  $\geq 2$  increased bilirubin
- Grade  $\geq 2$  increased ALT
- Grade  $\geq 2$  increased AST

The sponsor Medical Monitor will be notified promptly of AESIs. AESIs will be reported using the same process as for AEs.

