8.2. Clinical Laboratory Evaluations

The following laboratory tests will be performed for Part A and B:

Hematology	Absolute neutrophil count and differential, hematocrit, hemoglobin, mean corpuscular hemoglobin, mean corpuscular hemoglobin concentration, leukocytes-absolute counts and percentages (basophils, eosinophils, lymphocytes, monocytes, neutrophils), mean corpuscular volume, platelet count, red blood cell count, and red cell distribution width
Serum Chemistry	Alanine aminotransferase, albumin, alkaline phosphatase, aspartate aminotransferase, bilirubin (total + indirect and direct fractions), blood urea nitrogen, calcium, carbon dioxide, chloride, creatinine, gamma-glutamyl transferase, globulin, glucose, lactate dehydrogenase, phosphorus, potassium, sodium, total protein, uric acid, and creatine kinase
Urinalysis	Appearance, bilirubin, color, glucose, ketones, leukocytes, reflex microscopy (performed if dipstick is positive for protein or the blood value is 1+ or greater; and includes bacteria, casts, crystals, epithelial cells, red blood cells, and white blood cells), nitrites, occult blood, pH, protein, specific gravity, turbidity, and urobilinogen
Other tests	
Serology: Hepatitis B surface antigen, hepatitis C virus antibody, and human immunodeficiency virus antibody types 1 and 2 (screening only)
 
Urine drug screen (alcohol, amphetamines, barbiturates, benzodiazepines, cannabinoids, cocaine metabolites, cotinine, methamphetamines, methylenedioxymethamphetamine, and opiates [including heroin, codeine, and oxycodone])
 
Female participants: Follicle-stimulating hormone, urine pregnancy test/ serum pregnancy test (human chorionic gonadotropin)

The hematology, serum chemistry, and urinalysis tests will be performed at the timepoints indicated in the schedule of assessments (schedules of assessments can be found in [Section 13](#)).

All clinical laboratory test results will be presented in the data listings. Laboratory values that are outside of the normal reference range will be flagged in the data listings. Laboratory values will

also be graded per CTCAE V5.0, and the resulting grade for abnormal tests will be reported in the data listings.

Clinically significant laboratory test results and their associated adverse events or medical history, as recorded by the investigator on the laboratory eCRF, will be presented in a data listing.

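### AESIs are defined by laboratory grade but tabulated only from investigator-flagged records, so a qualifying liver result can be missed from the AESI tables

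*SAP*

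**What the plan says.** Protocol 6.2.2.6 and SAP 8.1 give the same three AESIs: increased bilirubin, ALT or AST, each at Grade 2 or above. Neither section adds a condition of clinical significance.

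For analysis, SAP 8.1 states: "Adverse events of special interest (AESIs) will be identified by the investigator on the eCRF". That flag feeds the Any AESI row of the overall AE summary and the table of treatment-emergent AESIs by system organ class and preferred term.

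SAP 8.2 handles the laboratory data separately. Values will "also be graded per CTCAE V5.0, and the resulting grade for abnormal tests will be reported in the data listings". The laboratory tables show actual values and changes from baseline, including the maximum and minimum post-baseline value, but nothing by grade.

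On how a result becomes an AE, Protocol 6.2 says: "If clinical significance is noted, the result and reason for significance will be documented and an AE reported on the AE page". Protocol 6.2.2.6 says: "AESIs will be reported using the same process as for AEs". Protocol 6.2.2, however, wants AEs "recorded in the eCRF and reported to the sponsor, regardless of their relationship to study drug or clinical significance", and adds: "If there is any doubt as to whether a clinical observation is an AE, the event should be reported". Protocol 6.2.1 sets a notification rule by grade alone: "The sponsor Medical Monitor will be contacted as quickly as possible for Grade 2 or above changes in blood AST, ALT, GGT, bilirubin".

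**The concern.** An objective threshold is counted through a judgement, although the objective data are already held and graded. Suppose an asymptomatic healthy participant has a transient Grade 2 ALT and the investigator, following Protocol 6.2, judges it not clinically significant. The result meets the AESI definition, but no AE record need exist to carry the flag.

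This matters because safety is a primary objective in both parts and the liver is where the drug's toxicity has been seen. Protocol 1.3 reports dose-limiting transaminase or bilirubin abnormalities of Grade 3 in 6 participants with cancer on repeated dosing, none of them at 1200 mg/day or below. The AESI tables are also the only planned tables that say how many participants reached Grade 2 or above in a liver test on each treatment. The treatments differ in exposure: in Part A the high-fat meal raised average AUC about 3-fold over the fasted state, both with cobicistat.

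**Working it through.** The documents state no figure on this point, so the check is mainly a comparison of text.

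**1. Definition against source of the count.** The definition is by grade (Protocol 6.2.2.6, SAP 8.1). The count comes from the eCRF flag (SAP 8.1). The graded laboratory values (SAP 8.2) are a second source for the same facts. SAP 8.1, 8.2 and 11 contain no derivation of AESIs from grades, no reconciliation of the two sources and no table by laboratory grade.

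**2. Must a Grade 2 result become an AE record?**

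| Section | Direction |
|---|---|
| Protocol 6.2 | AE reported when clinical significance is noted, so a result judged not significant may go unreported |
| Protocol 6.2.2 | AEs recorded whatever their clinical significance; report if in doubt |
| Protocol 6.2.2.6 | AESI by grade alone, but through the AE process |
| Protocol 6.2.1 | Medical Monitor contacted by grade alone; creates no AE record or AESI flag |

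The sections do not settle the question. Whether the result is flagged depends on which one the investigator follows.

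**3. What survives if it is not flagged.** The result stays in the listings with its CTCAE grade (SAP 8.2). It also enters the maximum post-baseline summary by treatment, and SAP 4 includes repeat and unscheduled assessments in that maximum. That summary describes the distribution of values; it does not count participants at Grade 2 or above.

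**4. Size of one missed participant.**
- Part A: all 12 planned participants receive each treatment, so 1/12 = 8.3 percentage points.
- Part B: 16 participants in 4 sequences at 1:1:1:1 gives 16/4 = 4 per sequence. Each treatment appears in 3 of the 4 sequences, so 3 × 4 = 12 are treated and 1/12 = 8.3 points.
- SAP 8.1 bases AE percentages on the safety set. If that means all 16 in Part B, 1/16 = 6.25 points.
- For scale, exact two-sided 95% intervals: 1/12 gives 0.2% to 38.5%; 0/12 gives 0% to 26.5%. The plan itself calls for no intervals here.

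**5. Chance of a miss (assumption only).** The documents give neither an AESI rate nor a miss rate. If each qualifying case goes unflagged with probability q, the chance that at least one of two is missed is 1 − (1 − q)². With q = 0.10 this is 1 − 0.81 = 19%; with q = 0.50 it is 1 − 0.25 = 75%.

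**The case against.** The strongest reply is that a sensible investigator would record these results anyway. Protocol 6.2 defines clinical significance broadly: medical relevance is enough, and so is a possible change in care, including closer observation. A result that requires contact with the Medical Monitor and is a named AESI is hard to call irrelevant. Protocol 6.2.2 points the same way, and Protocol 6.2.2.2 names laboratory values as a source of AEs. This stands in part: the text allows a miss but does not require one.

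A second reply is that a trial this small can be read from its listings, and that the maximum post-baseline summaries do not rest on judgement. SAP 8.2 even adds a version using a pre-treatment baseline. That also stands. A reader might infer that hepatic data are lost or that the whole hepatic signal is understated; the documents do not support this, because the gap is confined to the AESI rows.

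A reader might also infer that flagging will differ by treatment because the trial is open-label. That is possible, but nothing in the documents shows it.

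Finally, simply redefining the Any AESI row from laboratory grades would cause problems. The row would disagree with the AE-based table by system organ class and preferred term. Without an onset rule, one elevation spanning two periods would count against two treatments. SAP 8.2 measures total, direct and indirect bilirubin, so the fraction to be used would have to be named. These objections shape the fix; they do not remove the need for it.

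**Conclusion.** The concern holds in a limited form. The AESI tables rest on an investigator flag for an event defined by grade, the protocol sections that decide whether the flag is raised are in tension, and the SAP has no cross-check against grades it already holds. Qualifying results can be missed from those tables; the documents do not show that they will be.

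The size per missed participant is that in step 4 of the working and assumes full enrolment with balanced sequences. The expected number missed is unknown and may be zero. This is a low-cost improvement to a primary-objective safety display.

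**What to change.** **SAP 8.2.** Add a table, by treatment and overall, of maximum post-dose CTCAE grade and of the number of participants at Grade 2 or above, for ALT, AST and total bilirubin. Include repeat and unscheduled samples.
- Count a result under a treatment only if it is new or a worsening from that period's pre-dose grade.
- Assign it by the last-treatment rule already in SAP 8.1. In Part B, samples taken before dosing on Days 8 and 15 then belong to the preceding treatment.
- Give a supportive version using the pre-treatment baseline of SAP 8.2. Part A needs this most: it has no scheduled laboratory sample on dosing days, so the Day 4 or Day 11 value may serve as the next period's baseline.
- State the denominator for the Part B treatment columns: participants treated, or the whole safety set.

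**SAP 8.1.** Keep the AE-based Any AESI row and the table by system organ class and preferred term. Reconcile the laboratory-derived cases with the eCRF flag before database lock, and list any discrepancy.

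**Protocol.** Reconcile Section 6.2 with Sections 6.2.2 and 6.2.2.6, so that it is clear whether every qualifying result is to be recorded as an AESI.

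**Cost.** One derivation and one small table from data already collected and graded; no new samples. The hepatic count may become slightly less favourable.

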**Table 3-2 Study Description for Part B**

Treatment Period	Screening	Check-in	Dosing	Confinement
1	Day -28 to -1	Day -1	Day 1	Day -1 to Day 19 (EOS)
2	N/A	N/A	Day 8	
3	N/A	N/A	Day 15	

N/A, not applicable; EOS, end of study.

There will be a 7-day washout between dosing in each treatment period. EOS visit will be conducted on Day 19.

A screening evaluation will be performed to determine each participant's eligibility for the study approximately 28 to 1 days before the first dose. Participants eligible for participation will report to the study facility 1 day before dosing in Treatment Period 1 for check-in.

On Day 1 of Treatment Period 1, eligible participants will be randomized to 1 of 4 treatment sequences: A:C:D, B:D:A, D:B:C, C:A:B. On the first day of each treatment period, each participant will receive one of the following treatments according to the sequence in which he or she is randomized:

- Treatment A: 900 mg plixorafenib administered after overnight fast (fasted state).
- Treatment B: 900 mg plixorafenib administered following a high-fat high caloric meal (fed state-high fat meal).
- Treatment C: 900 mg plixorafenib administered following a low-fat meal (fed state-low-fat meal).
- Treatment D: 900 mg plixorafenib administered with 150 mg cobicistat following a low-fat meal (fed state-low-fat meal).

All participants will fast overnight (nothing to eat or drink except water) for at least 10 hours.

- Participants receiving Treatment A (fasted condition) will continue to fast for at least 4 hours after dosing.
- Participants receiving Treatment B will receive a high fat ( $\geq 50\%$  of the total caloric content of the meal), high caloric meal (approximately 800 to 1000 calories) for breakfast before dosing and this meal should derive approximately 150, 250, and 500 to 600 calories from protein, carbohydrate, and fat, respectively.
- Participants receiving Treatments C and D will receive a low-fat meal (approximately 400 to 500 total calories, with 25% of the total caloric content of the meal from fat) for breakfast before dosing.

All participants receiving Treatments B, C, or D must consume the entire meal within 30 minutes of serving; the percentage of meal consumed will be documented. Dosing must occur 30 minutes ( $\pm 5$  minutes) after the start of the meal. Participants receiving Treatments B, C, and D will receive their next meal no less than 4 hours after dosing.

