## 5. STUDY TREATMENTS

### 5.1 TREATMENTS ADMINISTERED

For Part A, each participant will be randomly assigned to 1 of 6 treatment sequences; the sequences will dictate the order in which each participant receives each of the planned treatments. Refer to Section 3 for a description of the treatment sequences.

For Part A, each participant will receive the following study treatments in a crossover design:

- Treatment 1: 900 mg plixorafenib ( $6 \times 150$  mg tablets) administered after overnight fast (fasted state).
- Treatment 2: 900 mg plixorafenib ( $6 \times 150$  mg tablets) + cobicistat ( $1 \times 150$  mg tablet) administered after overnight fast (fasted state).
- Treatment 3: 900 mg plixorafenib ( $6 \times 150$  mg tablets) + cobicistat ( $1 \times 150$  mg tablet) administered following a high fat, high caloric meal (fed state).

For Part B, each participant will be randomly assigned to 1 of 4 treatment sequences; the sequences will dictate the order in which each participant receives each of the planned treatments. Refer to Section 3 for a description of the treatment sequences.

For Part B, each participant will receive three of the following study treatments per randomization in a crossover design:

- Treatment A: 900 mg plixorafenib ( $6 \times 150$  mg tablets) administered after overnight fast (fasted state).
- Treatment B: 900 mg plixorafenib ( $6 \times 150$  mg tablets) administered following a high fat, high caloric meal (fed state-high fat meal).
- Treatment C: 900 mg plixorafenib ( $6 \times 150$  mg tablets) administered following a low-fat meal (fed state-low-fat meal).
- Treatment D: 900 mg plixorafenib ( $6 \times 150$  mg tablets) administered with 150 mg cobicistat ( $1 \times 150$  mg tablet) following a low-fat meal (fed state-low-fat meal).

There will be a washout of at least 7 days between dosing in each treatment period.

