- Participants receiving a ‘high fat’ treatment (900 mg plixorafenib administered following a high-fat high caloric meal) will receive a high fat ($\geq 50\%$ of the total caloric content of the meal), high caloric meal (approximately 800 to 1000 calories) for breakfast before dosing and this meal should derive approximately 150, 250, and 500 to 600 calories from protein, carbohydrate, and fat, respectively.
- Participants receiving a ‘low fat’ treatment (either 900 mg plixorafenib administered following a low-fat meal, or, 900 mg plixorafenib administered with 150 mg cobicistat following a low-fat meal) will receive a low-fat meal (approximately 400 to 500 total calories, with 25% of the total caloric content of the meal from fat) for breakfast before dosing.

Participants on ‘high fat’ or ‘low fat’ treatment must consume the entire meal within 30 min of serving; the percentage of meal consumed will be documented. Dosing must occur 30 min (± 5 min) after the start of the meal. Participants receiving ‘high fat’ or ‘low fat’ treatment will receive their next meal no less than 4 hours after dosing.

Participants will remain at the facility from check in (Day -1) to EOS and would be able to leave the facility upon satisfactory safety review by the investigator. Participants will be discharged from the study on Day 19 (Treatment Period 3).

The duration of the study for each participant, excluding screening period, will be approximately 20 days. Including screening period, the total study duration for each participant will be 48 days.

4. General Statistical Considerations

All statistical analyses will be conducted using statistical analysis system SAS® Version 9.4 or higher (SAS Institute, Cary, NC).

Descriptive statistics for continuous variables will include number of participants, mean, standard deviation (SD), median, minimum, and maximum, unless otherwise noted. For categorical variables, frequencies and percentages will be presented.

All tables, listings, and figures (TLFs) will be presented by part, and where applicable either; overall, or by treatment, or by treatment and overall, or by treatment sequence.

When presented by treatment, the treatments below will be used for presentations:

- Part A:
 - 900 mg plixorafenib (Fasted)
 - 900 mg plixorafenib + 150 mg cobicistat (Fasted)
 - 900 mg plixorafenib + 150 mg cobicistat (Fed)
- Part B:
 - 900 mg plixorafenib (Fasted)
 - 900 mg plixorafenib (High Fat)
 - 900 mg plixorafenib (Low Fat)

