4.1. Sample Size

The number of participants is based on clinical and practical considerations and not on a formal statistical power calculation. The total sample size of 12 participants in Part A and 16 participants in Part B is considered sufficient for the objectives of the study.

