4.3. Analysis Sets

Part A and Part B

The safety set will include all participants who received at least 1 dose of plixorafenib.

The PK population will include participants who receive at least 1 dose of plixorafenib and have sufficient concentration data to support accurate estimation of at least 1 PK parameter. Participants who experience vomiting within 2 times the median T_{max} after study drug dosing will be excluded from the PK analysis.

For Part A, all enrolled participants may be used for analysis. This set will include all participants who, according to the study investigator on the electronic case report form (eCRF), had met all eligibility criteria and were ready for randomization, regardless of whether they were then randomized or not.

5. Participant Disposition

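### SAP 8.1 gives no by-treatment or by-sequence denominator for TEAE percentages; read literally, Part B by-treatment percentages would be 0.75 times the rate among those treated

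*SAP*

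**What the plan says.** SAP 8.1 (Adverse Events) plans the TEAE tables as follows: "The TEAEs will also be summarized, by treatment and overall population, by system organ class (SOC), preferred term (PT), by CTCAE toxicity grade". It adds a further TEAE table by treatment sequence and overall. For these tables it states one denominator: "Percentages will be based on the number of participants in the safety set".

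SAP 4.3 (Analysis Sets) defines the set: "The safety set will include all participants who received at least 1 dose of plixorafenib". There is no version of the set by treatment or by sequence. The opening of SAP Section 8 bases all safety summaries on this set, and Protocol 7.3.2 gives no denominator of its own.

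The numerator is treatment-specific. Under SAP 8.1, "a TEAE will be assigned to the last treatment received prior to the assessment/observation as below", and a participant counts once per level of summarisation.

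For Part B, Protocol 5.1 says that "each participant will receive three of the following study treatments per randomization in a crossover design".

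**The concern.** The numerator of a by-treatment percentage can include only participants who received that treatment. The denominator, read literally, also includes participants who never did. In a complete crossover without dropout the two groups coincide, so the wording does no harm. In Part B they differ by design, because each participant skips one of the four treatments.

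Safety is a primary objective of both parts, and the by-treatment TEAE tables, including those for related TEAEs and AESIs, are its main summary. Two programmers could follow SAP 8.1 in good faith and produce different percentages from the same data. Plixorafenib alone in the fasted state is given in both parts. On the literal reading it would be divided by 12 in Part A and by 16 in Part B, although planned exposure is 12 in each.

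**Working it through.** The documents state no AE percentage and no number exposed per treatment, so there is no figure of the plan's own to reproduce. The check counts exposure from the design.

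**Inputs**
- Planned size, SAP 4.1: 12 participants in Part A and 16 in Part B.
- Part B sequences, Protocol 3.2: "randomized to 1 of 4 treatment sequences: A:C:D, B:D:A, D:B:C, C:A:B". SAP 3.2 gives the allocation as 1:1:1:1.
- Part A, Protocol 3.1 and SAP 3.1: six sequences, equal allocation, all three treatments in every sequence.
- Separate tables for the two parts, SAP Section 4: "All tables, listings, and figures (TLFs) will be presented by part". The Part B safety set is therefore 16 as planned, not 28.

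**Step 1: number exposed per treatment, full completion**
- Part B: 16/4 = 4 per sequence. A is absent only from D:B:C, B only from A:C:D, C only from B:D:A and D only from C:A:B. Each treatment is therefore in 3 sequences, and 3 × 4 = 12 of 16 are exposed.
- Part A: 12/6 = 2 per sequence. Each treatment is in all 6 sequences, and 6 × 2 = 12 of 12 are exposed.

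**Step 2: literal percentage against rate among those treated**

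Ratio = (x/N safety set) / (x/n exposed) = n/N. In Part B this is 12/16 = 0.75, so the relative understatement is 1 − 0.75 = 25%.

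| Participants with event (Part B, one treatment) | Literal, x/16 | Among those treated, x/12 |
|---|---|---|
| 1 | 6.25% | 8.33% |
| 3 | 18.75% | 25.0% |
| 6 | 37.5% | 50.0% |
| 12 | 75.0% | 100% |

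No Part B treatment column could exceed 75%. In Part A the ratio is 12/12 = 1.

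**Step 3: by-sequence table**

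The same sentence read literally divides at most 4 by 16 in Part B (ceiling 25%) and at most 2 by 12 in Part A (ceiling 16.7%), even if every participant in the sequence has the event.

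**Step 4: dropout**

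A participant dosed once stays in the safety set. In Part B, one unreplaced dropout after period 1 or 2 leaves 11 of 16 exposed for each missed treatment: 1 − 11/16 = 31.25%. The other treatments stay at 25%, so the factor is no longer uniform. In Part A, one unreplaced dropout gives 1 − 11/12 = 8.3% for each missed treatment. Protocol 4.4.3 allows replacement, which would change these counts.

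**Step 5: overall columns**

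Every safety-set participant can contribute, so the stated denominator is right there.

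**The case against.** The strongest reply is that the sentence names the population and leaves each column to use its own N. Several things support this. The literal reading makes the by-sequence table meaningless (Step 3), which cannot be what the authors wanted. SAP 8.2 tabulates laboratory values by treatment for the safety set, where only participants with data under a treatment can contribute, so the term already serves as a population filter. SAP 5.1 counts the recipients of each Part B treatment, so the authors knew that exposure differs from the safety set. All of this stands, and it makes column-specific denominators a plausible intention. It does not put that rule in the text.

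The consequences are also limited even on the literal reading. The overall AE summary shows counts beside percentages, the disposition table gives the number exposed, and all AEs are listed, so a reader can recompute any rate. No safety threshold or decision rule uses these percentages. This stands too, and it lowers the severity.

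A reader might infer more than the documents support:
- **That Part B rates will be understated by a quarter.** The SAP never says that a treatment column is divided by all 16. This is one reading of an incomplete rule.
- **That the error is 25 percentage points.** The figure is relative: 25.0% becomes 18.8%.
- **That comparisons between Part B treatments are biased.** With full completion the factor is 0.75 in all four columns, so their ratios are unchanged.
- **That Part A rates are wrong.** Every Part A participant is planned to receive all three treatments, so its by-treatment columns change only if someone drops out.
- **That a planned comparison across parts is compromised.** Tables are presented by part, and SAP Section 4 mentions pooling by treatment only as a possible exploratory analysis.

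**Conclusion.** The point holds as an incomplete denominator rule that gives a wrong result if followed literally. On that reading, Part B by-treatment TEAE percentages are 0.75 times the rate among those treated, and by-sequence percentages are capped at 25% in Part B and 16.7% in Part A. The 0.75 assumes 16 participants, 4 per sequence, full completion and no replacements. Column-specific denominators may well be intended, so the understatement is a risk that the wording permits and not an established error. It should be fixed, but it is not a must-fix: counts and exposure are reported, no decision depends on the percentages, and the overall columns are correct as written.

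**What to change.** Replace the denominator sentence in SAP 8.1 with:

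*By-treatment percentages are based on safety-set participants in that part who received that treatment; by-sequence percentages on safety-set participants in that sequence; overall percentages on all safety-set participants in that part.*

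Apply the same rule to the overall AE summary, and show the matching N in each column header. If the exploratory pooled tables are produced, state their denominator in the same way.

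The cost is one sentence and a header N. The number receiving each treatment is already planned for the disposition table in SAP 5.1, so no new data are needed and trial conduct does not change. The edit should be made before the tables are programmed.
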